 - a. Serial Skeletal Muscle Ultrasounds at days 0, 3, 5, ICU discharge, hospital discharge Muscle thickness, size and echogenicity in the vastus and the rectus femoris muscles
 - b. Serial Plasma at days 0, 1, 3, and 5 and ICU and hospital discharge
 - i. Plasma acylcarnitine profile
 - ii. Will be banked for future studies
 - c. Blood on 1st day of exercise (for 5 intervention patients only) will be evaluated for leukocyte kinetics in response to exercise (exploratory analysis) based on animal data. This is completed.

- 4) Pilot study: To determine the effects of exercise on energy utilization, mitochondrial function, and CPT-1 activity. Phase II: To determine the effects of exercise on energy utilization.
 - a. Continuous non-invasive CO2 monitoring, day 0 through day 5
 - b. Accelerometer activity monitor, day 0 through 2 weeks post-discharge.
 - c. Nutritional Assessments, blood sugar levels, day 0 through ICU discharge

TABLE 5: TESTING BATTERY	Day 0	Day 1	Day 3	Day 5	ICU D/C	Hosp D/C	Phone: 3 months	Phone: 6 months
Aim 1: Physical Function:								
Feasibility	х	х	х	Х	Х	Х	х	х
MAT-sf	Х				Х	Х		
SPPB					Х*	Х		
Handgrip/ quad strength					Х	Х		
MoCA / MoCA Blind					Х	Х	х	х
Aim 2 Muscle Mass:								
Ultrasound	Х		Х	Х	Х	Х		
Aim 3: Quality of Life:								
SF-36						Х	Х	х
Exploratory Outcomes:								
ICU LOS					Х			
Hospital LOS						Х		
Vent-Free Days (28)					Х	Х		
Healthcare Utilization							Х	х
Mortality					Х	Х	Х	х
Blood	Х	Х	Х	Х	Х	Х		
Energy	Х	Х	Х	Х	Х	Х		

Updated Testing Battery:

NB—Inpatient assessments may be completed up to 1 day before or after the specified time point, and may be carried over to another assessment. Outpatient assessments may be completed up to 2 weeks before or after the specified time point. Muscle biopsies may be performed up to 1 day before or 2 days after the specified time point.

Data Collection for demographics and baseline information: Demographic Information will be obtained on all patients. Additionally, the Acute Physiology and Chronic Health Evaluation (APACHE), Charlson index, and the comorbidity indices will be calculated. Other variables which will be collected will include medications and information about ICU and hospital stays.

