- 2) SPPB, handgrip strength/dynamometry, calorimetry, ICU and hospital lengths of stay, healthcare utilization (SPPB), ventilator-free days, mortality, and SF-36 and MoCA scores will all be analyzed with descriptive statistics. Tests for trend will be evaluated and adjusted analyses will also be performed. Analysis of co-variance will be used, adjusted for age, gender, and BMI and other adjusted analyses will be performed as necessary. We will also explore the longitudinal effect of the intervention with linear mixed effect models.
- And 4) Muscle ultrasound measures, skeletal muscle biopsy measures, and plasma analyses will also be analyzed with descriptive statistics, tests for trend including with linear mixed effect models, and adjusted analyses.

In sum, results will be analyzed initially using descriptive statistics. Comparison between groups will be done using chi square tests for proportions, and t-tests or ANOVA procedures for continuous variables. Regression analysis will be performed to identify independent outcome predictors. Other inferential statistical analysis will be conducted as appropriate.

Phase II: The primary analysis is to compare SPPB at ICU discharge between the two groups using analysis of covariance (ANCOVA), adjusted for age, gender, and BMI. Under our assumptions of attrition (estimated at 15%) and mortality (SPPB=0 if patient has passed), with the current sample size (n=42), we will be able to detect an effect size of 0.98 or higher in the SPPB at ICU discharge with a power of 81% and a two-sided significance level of 0.05. This effect size is based on our pilot data and corresponds with the known minimal clinically important difference in SPPB of 0.5-1.3.^{15,16} We will perform similar analyses for SPPB at hospital discharge and explore the longitudinal effect of the intervention, using linear mixed effect models to compare the trajectories of SPPB over time. We will analyze secondary outcomes including hand grip, quadriceps dynamometry, RF CSA and echogenicity, quadriceps depth, TA depth and echogenicity, and QOL in a similar fashion. For this study, the services of the Pepper Center Biostatistics and Research Information Systems Core will be used.

Human Subjects Protection

Please see attached document.

Subject Recruitment Methods

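### Secondary ultrasound outcomes: the plan schedules a Day 0 scan but does not name it as a covariate or say how it enters the mixed models; using it is a nearly free gain in precision

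*Combined protocol and SAP*

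**What the plan says.** The Analytical Plan, Phase II, compares SPPB at ICU discharge between arms "using analysis of covariance (ANCOVA), adjusted for age, gender, and BMI". It then extends the work to hospital discharge and to longitudinal models, "using linear mixed effect models to compare the trajectories of SPPB over time". The secondary outcomes follow in one sentence, which ends "RF CSA and echogenicity, quadriceps depth, TA depth and echogenicity, and QOL in a similar fashion". No separate covariate list is given for ultrasound.

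The schedule differs by outcome. The Updated Testing Battery (Table 5) has no Day 0 entry for SPPB, handgrip and quadriceps strength, or SF-36. Ultrasound does have one. Outcome Measure(s), item 3a, lists "Serial Skeletal Muscle Ultrasounds at days 0, 3, 5, ICU discharge, hospital discharge" and describes the content as "Muscle thickness, size and echogenicity in the vastus and the rectus femoris muscles". The TA muscle appears in the Phase II analysis but not in item 3a.

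The Phase I text offers ultrasound "tests for trend including with linear mixed effect models, and adjusted analyses" but names no covariate. On timing, the note under Table 5 says "Inpatient assessments may be completed up to 1 day before or after the specified time point, and may be carried over to another assessment". Interventions and Interactions places cycling within 48 hours of randomization, subject to the safety criteria.

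**The concern.** The covariate set was written for an outcome that cannot have a baseline value, and was then applied to outcomes that do have one. Taken literally, the ultrasound ANCOVA would adjust for age, gender and BMI and leave out the variable likely to predict the discharge scan best: the same muscle measured at entry.

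The effect on muscle mass is a listed objective and Aim 2 of Table 5, with at most 21 patients per arm. The trial also aims to supply effect sizes for a larger study, so interval width matters here.

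The mixed models may use Day 0 in part, but the plan leaves their form open. Day 0 could be a response with free arm means, a covariate, or a visit at which the arm means are held equal. The contrast could be at a visit, a change or a slope. These choices differ in precision and are better fixed before the data are seen.

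**Working it through.** **Inputs.** From the documents: 21 per arm, 15% attrition, effect size 0.98 (read as standardized), 81% power, two-sided 0.05, three covariates. Assumed: r, the Day 0-to-discharge correlation given age, sex and BMI, at 0.3, 0.5, 0.7 and 0.8. It may differ between size, depth and echogenicity.

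**The plan's own figure.** 21 × 0.85 = 17.85, so about 18 per arm. Noncentral-t power at 0.98 is 81.5%, or 81.3% after removing 3 degrees of freedom for covariates. The stated 81% reproduces. It concerns SPPB; no precision figure is given for ultrasound.

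**ANCOVA with and without Day 0.** Adding Day 0 multiplies residual variance by 1 − r². Allowing for chance imbalance in k covariates multiplies the variance of the arm effect by (N − 3)/(N − k − 3). With N = 36:

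- k = 3: 33/30 = 1.100, with 31 df
- k = 4: 33/29 = 1.138, with 30 df

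Interval-width ratio = (t₃₀/t₃₁) × √(1.138/1.100) × √(1 − r²) = 1.018 × √(1 − r²). Break-even is where this equals 1, at r = 0.19. With an illustrative 12 per arm the multiplier is 1.033 and break-even is r = 0.25.

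Power is shown for an assumed difference of 0.5 residual SD. Without Day 0 it is 28% at 18 per arm and 19% at 12.

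| r | Width ratio, 18 per arm | Power, 18 per arm | Power, 12 per arm |
|---|---|---|---|
| 0.3 | 0.972 | 30% | 19% |
| 0.5 | 0.882 | 35% | 23% |
| 0.7 | 0.727 | 48% | 31% |
| 0.8 | 0.611 | 62% | 41% |

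In simulation at 18 per arm, mean interval width fell from about 1.41 SD to 1.25 (r = 0.5) and 1.03 (r = 0.7). Type I error stayed at 0.042 to 0.054 with or without Day 0.

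**If the mixed model contrasts change from Day 0.** The variance is 2(1 − r), against 1 − r² with adjustment. The saving is (1 − r)/2 = 35%, 25%, 15%, 10%. With the imbalance factors above, 1 − (1.138/1.100)(1 + r)/2 gives 33%, 22%, 12%, 7%.

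**If it contrasts arms at a visit with free arm means.** With n of 21 scanned at discharge, a likelihood-based model still uses Day 0 from patients without a discharge scan. The large-sample variance per arm is (1 − r²)/n + r²/21, against (1 − r²)/n when the Day 0 means are held equal. At n = 18 and r = 0.5: 0.0417 + 0.0119 = 0.0536, a saving of 0.0119/0.0536 = 22%. Over the four values of r:

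- 18 of 21 scanned: 8%, 22%, 45%, 60%
- 12 of 21 scanned: 5%, 16%, 35%, 50%

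**Late Day 0 scans.** Suppose half of the intervention-arm Day 0 scans follow a session that shifts the reading by 0.2 SD (assumed). If they are kept, the bias is −r × 0.5 × 0.2, so a true 0.50 is estimated as 0.43 at r = 0.7.

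Now suppose they are discarded and imputed without regard to arm, and those dropped average 0.23 SD above the mean (assumed). The retained half averages −0.23 and the pooled observed mean is (0.5 × −0.23)/1.5 = −0.077. The intervention-arm baseline mean becomes (−0.23 − 0.077)/2 = −0.153, and the estimate is 0.50 + 0.7 × 0.153 = 0.61. If dropping is unrelated to baseline, there is no bias.

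**The case against.** The strongest reply is that the plan is under-specified and does not actually leave Day 0 out. It lists no ultrasound covariates, and the sentence that carries the analysis over directly follows one about trajectory models. With scans on days 0, 3 and 5 and at both discharges, a trajectory model would naturally include Day 0. This stands. A reader might infer that the plan excludes the Day 0 scan, and the documents do not support that. They support only that its role is unstated and that no covariate list includes it. The open-ended adjusted analyses in the Phase I text do not fill the gap.

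The size also rests on an unknown r and an unstated contrast. That stands too. At 12 per arm and r = 0.3, ANCOVA power stays at 19%.

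It is tempting to apply the full r² reduction (9%, 25%, 49%, 64%) to a by-visit mixed model with free arm means. That holds only with complete data, and the savings are smaller once discharge scans are missing.

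Finally, late Day 0 scans are a possibility under the visit window and not a documented event. A rule that discards them could do harm. Study sessions start by protocol in the intervention arm, while controls receive therapy as ordered. The exclusion would therefore occur after randomization, fall mainly on one arm, and might track fitness. No section says that control session times or scan clock times are recorded.

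**Conclusion.** The point holds as a low-cost improvement in precision for secondary outcomes. Using the Day 0 scan in the ANCOVA narrows the interval by about 3% to 39% for r from 0.3 to 0.8 at 18 per arm, and loses slightly below r of about 0.19. Against a mixed model the variance saving is 10% to 35% or 8% to 60%, depending on the contrast (the first before chance imbalance, the second with 18 of 21 scanned).

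The 18 is borrowed from the SPPB calculation, where deaths count as zero ("mortality (SPPB=0 if patient has passed"). Ultrasound has no such convention, so fewer scans are likely.

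A reader might infer that the omission biases the arm comparison or weakens the primary analysis. Neither follows. Simulated type I error is unaffected, and SPPB has no Day 0 value, so its analysis, 81% power and N=42 are unchanged. Nor does the Day 0 covariate cure the survivors-only nature of the discharge scans.

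**What to change.** Add two or three sentences to the Analytical Plan, Phase II:

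- For RF CSA, RF echogenicity and quadriceps depth, include the Day 0 value of the same measure as a covariate beside age, sex and BMI in the ANCOVA. Do the same for the TA measures only if a Day 0 TA scan exists.
- In the mixed models, enter Day 0 as a covariate or constrain the arm means to be equal at Day 0, and name the contrast (visit, change or slope).
- Aim to take the Day 0 scan before the first study session. Where times are recorded, report by arm how many were taken after it. Keep late scans in the main analysis and examine them in a sensitivity analysis; do not discard and impute them.
- Report the number alive and the number scanned per arm at each visit, and describe discharge results as a comparison among survivors with scans.

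The cost is one degree of freedom per ANCOVA, and an interval about 2% wider at 18 per arm if r is zero. No extra patients are needed, and no extra scans of the vastus or rectus femoris. The timing report needs scan and session times, which the documents do not confirm are collected in both arms.
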